### Research Questions and Hypotheses:

*Specific Aim 1: To determine the impact of service dogs and determine who benefits the most.*

**Hypothesis 1A:** Individuals partnered with SDs will have greater improved mental health over time (Primary outcome will be the PCL checklist. Secondary mental health will be quantified by scores on depression and alcohol use).

**Hypothesis 1B:** Individuals partnered with SDs will have improvements over time in secondary factors of physical, psychosocial, and socioeconomic variables. The secondary factors are defined as follows: 1) physical factors: co-morbidities, medication use, sleep 2) psychosocial factors: community participation, quality of life and 3) socioeconomic factors: demographic and health care utilization and out-of-pocket health care expenses.

*Specific Aim 2: To determine costs associated with total health care utilization and mental health care utilization among Veterans with mental health disorders needs and service or therapy dogs.*

**Hypotheses 2A:** Individuals partnered with SDs will have decreased mental health care utilization over time.

**Hypotheses 2B:** Individuals partnered with SDs will have decreased total health care utilization over time.

*Specific Aim 3: To determine recommendations for providing service dogs to Veterans.*

Develop a strategic plan to provide service dogs to Veterans. A consensus meeting will be planned and will include all investigators of the project along with key individuals from funding agency to discuss findings of study.

*Secondary Aim:* To compare study findings to another VA funded study that is providing dogs as pets to Veterans with PTSD. Both studies are using similar measures to assess mental and psychosocial factors. Data will be compared across groups (SD to dog as a pet) to determine if the highly trained dogs help the Veteran more than having a dog as a pet.

*Projected Time Table*

Training of SDs is time intensive and expensive, with limited numbers of dogs who actually graduate. We will work with vendors to obtain the dogs, but recognize that there may be a significant waiting period prior to pairing. To demonstrate maximum treatment benefits, the data collection phase of this three-year study will be conducted for a minimum 18 months (maximum of 24 months for early enrollees) as we feel the acclimation period for the human-animal bond is longer than 18 months. This allows sufficient time for statistical analyses.

*Timeline*

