**Analysis:** The distribution of each variable will be examined for outliers to determine if transformations (to normalize data) are necessary. Initially, means  $\pm$  SD, and medians, will be calculated for all continuous measures (e.g., age, psychological scales). Frequencies and percent will be determined for categorical variables (e.g., gender, race, etc.). Variables considered ‘confounders’ (demographic and dog predisposition questionnaires) would be compared across time for the relevant hypotheses. Categorical variables (e.g., gender, race, disability) will be compared across groups using chi-square. Continuous variables (years of disability, dog predisposition scores) will be compared using ANOVA. Baseline differences will be noted and controlled for in additional analyses. A significance level of ( $\alpha < 0.05$ ) will be used for all analyses. All data will be managed as intent to treat.

Statistical Analyses are presented below by hypothesis:

**Hypothesis 1A:** *Individuals partnered with SDs will have greater improved mental health over time.* Baseline data will be examined. Observed significant differences will be used as covariates in modeling, they will be controlled in subsequent analysis. For this hypothesis, a linear repeated measures mixed model will be used to determine changes over time between groups. PCL-checklist scores will be considered the dependent variable. Baseline PCL-C scores will be introduced in all models as covariates. These scores are continuous. The use of mixed models allows for control of covariance data expected in clustered and repeatedly sampled data, and missing data. We expect the SD group to have greater functional independence and community participation at the end of the study.

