**Hypothesis 1B:** *Improvements in secondary factors of physical, psychosocial, and socioeconomic variables will be seen in the SD group over time.* Variables within the physical (medication, comorbidities), psychosocial (affect, depression, loneliness) and socioeconomics (healthcare utilization) will be compared over time and will be assessed for each variable of interest using a repeated measures mixed model for dependent variable (DV) scored a continuous scale and generalized estimating equations (GEE) models for DV variables scored as a categorical. Dependent variables for all models will be scale or subscale scores. The within-participants variable will be the score at each time point (baseline, 3, 9, 12, 18 and 24 months). If significant differences exist at baseline for any confounding variables, that factor will be controlled for in the analysis. We expect to show improvements in all characteristics over the course of the study.

We will also complete a multivariate logistic regression to determine predictors of success (dichotomized higher scores after 18 months on function and participation). We expect that improvements in psychosocial factors (e.g, community participation) will result. We expect the data to be normally distributed; therefore, linear regression will be used. Results from the previous hypotheses (1B) will be used to determine which predictor variables are entered into the regression model; any variable with a  $p$ -value less than 0.10 will be considered. Highly related variables will be entered into the model separately. Any confounders significant at baseline will

Dogs and PTSD: V11: 11.26.14

be controlled for in the models. In addition, we will repeat the multivariate logistic regression analysis described above with group (SD vs. control) as a primary fixed variable. We expect that subjects paired with a SD will demonstrate increased improvement in psychosocial factors.

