We expect some individuals to benefit more than others. We hypothesize that individuals with greater limitations will have the most improvement when provided with an SD. Consequently, we will conduct a sub-analysis of the SD group. We acknowledge this is an exploratory analysis and the power is limited. The hypothesis we will test is individuals who score lower in psychosocial factors (e.g. community participation) at baseline will show greater improvements in those characteristic than individuals who scored higher. Therefore we will use the subcomponents scores of continuous measures and dichotomize them at a clinically meaningful point (e.g.,  $\geq 80 \geq 75^{\text{th}}$  percentile) at the baseline measure. All individuals will be put into one of two groups based on this cutpoint. Repeated measures analyses will be completed on all continuous variables with the between factor being the two groups and the within measure equaling variables of physical, psychosocial and economic characteristics.

In addition, we will conduct an exploratory analysis to determine whether relationships exist between group status (SD vs. control), demographic variables (age, gender, living arrangements, marital status, etc.) and the outcomes of interest – mental health (, PCL-C) and psychosocial factors (e.g. community participation). Categorical demographic variables will be analyzed using a chi-square for variables that are dichotomous, and one-way ANOVAs will be used for continuous variables that have multiple categories. Continuous demographic variables (e.g., age) will be compared to the outcomes using correlations: Pearson for normally distributed variables and Spearman rho for not-normally distributed variables. Sub-analysis will examine the relationship between the outcomes of interest and the physical, psychosocial and economic variables. Correlation analysis will be used to determine significant relationships. Two separate multiple regression models will be developed using any variables significant at a  $p$ -value  $< 0.10$  in the univariate analysis. The outcomes will be from the 18-month visit, whereas the predictor variables will be those recorded at baseline. These analyses will be used to describe those characteristics of Veteran's most likely to benefit from obtaining a SD compared to control subjects.

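### Splitting continuous baseline scores into two groups discards roughly a third to a half of their information in the exploratory who-benefits sub-analysis; same-scale tests also need protection from regression to the mean

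*Combined protocol and SAP*

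**What the plan says.** Specific Aim 1 is "To determine the impact of service dogs and determine who benefits the most". Under Hypothesis 1B, the analysis section plans a sub-analysis of the service-dog group for this purpose. Its hypothesis is that "individuals who score lower in psychosocial factors (e.g. community participation) at baseline will show greater improvements in those characteristic than individuals who scored higher".

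The method is to take continuous scores and cut them: "Therefore we will use the subcomponents scores of continuous measures and dichotomize them at a clinically meaningful point". The example given for the cut combines a value of 80 with the 75th percentile, and the text is garbled there, possibly by PDF reading. No threshold is set for any instrument. Then "All individuals will be put into one of two groups based on this cutpoint", and "Repeated measures analyses will be completed on all continuous variables with the between factor being the two groups". The outcomes are the physical, psychosocial and economic variables, so each split is run against other scales as well as its own.

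The plan says of this work: "We acknowledge this is an exploratory analysis and the power is limited". It gives no effect size, sample size or power for it.

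**The concern.** The hypothesis is graded: the lower the starting score, the larger the gain. A two-group factor treats everyone on one side of the cut as alike. It therefore cannot show how benefit changes with severity, and it uses only part of the information in the score. With a 75th-percentile cut, three quarters of the sample share one group, so any gradient among them is invisible. The scales are numeric (for example, the Community Integration Questionnaire runs 0 to 29), and the plan gives no reason that requires a split.

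A second problem affects the stated hypothesis. The same scale defines the baseline group and supplies the change. Low scorers then tend to rise and high scorers to fall even if the dog helps everyone equally. This affects the split and a continuous score alike, so replacing one with the other is not enough.

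**Working it through.** **No figure to reproduce.** The nearest power statement (65 per group, over 80% power, under Hypothesis 1) concerns another comparison and gives no effect size.

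**Inputs.**
- Sample size (Sample section): up to 220 recruited with 33 drop-outs leaves 220 − 33 = 187. The same section expects 200 completers, so both are used.
- Significance level: 0.05 in the plan; two-sided assumed.
- Autocorrelation between repeated assessments: 0.80, from the power paragraph in the Sample section.
- Normality: assumed for baseline scores. The plan expects it only for its regression ("We expect the data to be normally distributed; therefore, linear regression will be used").
- Correlation r between baseline score and change: not in the plan; shown over 0.10 to 0.30.

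**Step 1: information kept by one cut.** For a normal score linearly related to change, the relative efficiency of a cut at quantile q is φ(z)² / [q(1 − q)], where z is the normal quantile at q.
- Median: 0.3989² / 0.25 = 0.637, a loss of 36%.
- 75th percentile: 0.3178² / 0.1875 = 0.539, a loss of 46%.
- 80th percentile: 0.2800² / 0.16 = 0.490, a loss of 51%.

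At the 75th percentile, 187 Veterans carry the information of about 187 × 0.539 = 101, and 200 that of about 108. For other shapes cut at the 75th percentile, simulated losses were 36% (right-skewed beta, exponential), 42% (rounded scores on a 0–29 scale), 44% (uniform) and 55% (left-skewed beta).

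**Step 2: power where baseline score and outcome are different measures.** The test is a two-sided t test of the correlation, with noncentrality r√n / √(1 − r²). After the split, r is replaced by r × √0.539 = 0.734r. At n = 187 and r = 0.20, noncentrality is 2.79 for the continuous score and 2.03 for the split.

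| Assumed r | n = 187: continuous / split | n = 200: continuous / split |
|---|---|---|
| 0.10 | 28% / 17% | 29% / 18% |
| 0.15 | 54% / 33% | 57% / 34% |
| 0.20 | 79% / 52% | 82% / 55% |
| 0.25 | 94% / 72% | 95% / 75% |
| 0.30 | 99% / 87% | 99% / 89% |

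**Step 3: the null where they are the same measure.** Let X be baseline and Y a later score, with equal variances, correlation ρ and no differential benefit. Then cov(X, Y − X) is proportional to ρ − 1 and var(Y − X) to 2(1 − ρ), so corr(X, Y − X) = −√[(1 − ρ)/2]. At ρ = 0.80 this is −√0.10 = −0.316, already larger in size than any r in the table. After the split it is 0.734 × 0.316 = 0.232 in size. At n = 187 the noncentralities are 4.56 and 3.26, which give rejection rates of about 99% (continuous) and 90% (split). Simulation of this null gave the same figures. Under first-order decay the correlation falls with the interval (0.80⁴ = 0.41), and both tests then reject about 100% of the time.

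**The case against.** Five points can be made for the plan.

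*The analysis is exploratory and admits limited power.* This stands, and it caps the importance of the point. It does not justify the less efficient method.

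*The cut is only an example.* This stands against any single headline figure. A reader might infer that the plan loses 46%. The plan fixes no cut, and that figure needs normality, linearity and the 75th percentile.

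*Another analysis already keeps baseline predictors continuous.* The next paragraph of the plan uses correlations and multiple regression of 18-month outcomes on baseline variables. This partly stands. That analysis addresses the 18-month outcome rather than change by baseline level, and it is worded as a comparison with control subjects, a group the Design section eliminates. It does not replace this test.

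*The main danger for the stated hypothesis is a false gradient, not a missed one.* This stands in full. A reader might infer that the Step 2 power figures apply to that hypothesis, that Type I error is near 5% either way, or that a continuous baseline-by-time term cures the problem. Step 3 contradicts all three: the continuous term rejects the artefact more often than the split does.

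*Nothing else depends on this result.* A reader might infer that it determines the recommendations under Specific Aim 3. The plan says only that a consensus meeting will discuss the study's findings.

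**Conclusion.** The point holds as a minor improvement to an exploratory analysis. A single cut discards about 36% to 51% of the information between the median and the 80th percentile under normality and linearity, and 36% to 55% at the 75th percentile for the other shapes tried. The resulting power gain (79% against 52% at n = 187 and r = 0.20) belongs only to pairs in which the baseline score and the outcome are different measures, and it rests on an assumed correlation. For the same-measure hypothesis neither method gives an interpretable test as planned. That conclusion uses the plan's own autocorrelation and assumes stable variance.

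**What to change.** Revise the sub-analysis under Hypothesis 1B as follows.

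1. Enter each baseline score as a centred continuous variable, with a quadratic or spline term to check linearity. Report predicted values at the 25th, 50th and 75th percentiles of the baseline score. Use any two-group split for display only.
2. Model the post-pairing visits as the response, with the outcome's own baseline as a covariate. The plan already uses baseline PCL as a covariate under Hypothesis 1A, whereas Hypothesis 1B lists baseline among the repeated time points. Test the continuous modifier and its interaction with time.
3. Where modifier and outcome are the same scale, state that the baseline-by-time slope will not be read as differential benefit. Use the repeated pre-dog assessments (every three months, then every six after 24 months) to test whether the baseline–change relation after pairing exceeds that over the waiting period. Compare intervals of equal length, because the artefact grows as the correlation decays.

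The cost is wording and model terms; no new data, visits or Veterans are needed. The downsides are a functional-form assumption, which the check in item 1 addresses, and slightly more complex reporting.

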### Other Forms

Form	Purpose	When Completed	Who Completes
Home environment checklist	Checklist to assess home environment prior to dog placement	Pre-pairing home visit	Study Team Dog Trainer
Dog Care Test	Test knowledge of dog care and responsibility	After completion of Dog Care Course	Veteran
Service Dog Post Pairing Evaluation	Assess pairing and identify potential health or behavior problems in dogs	One week post pairing, months 1, 2, 3, 6, 9, 12, 18, 24	Study Team Dog Trainer at home visit
Veterinarian Checklist	Assess dog's health	Once per year	Veterinarian caring for each dog
Veteran Guide for Veterinary Care	Provides information to Veteran about maintain dog's health	Provided when Dog Care Course is completed	Information provided to Veterans
Home visit information sheet	Provides information to Veterans about how and why the home visit is done	Provided after IC, prior to home visit	Information provided to Veterans

Service Dog Questions	Veteran's subjective report about the dog's behavior and Veteran's satisfaction with the dog	Months 3, 6, 9, 12, 18, 24	Study team member present at home visit
-----------------------	--	----------------------------	---

Unless otherwise noted, all measures are completed at all visits.

\*\*Data for these items will be abstracted from medical record

Mental Outcomes: Outcomes for the main hypotheses will be measured with the following measure using the PTSD Checklist (PCL). PTSD Checklist is a 17-item self-report measure of the 17 DSM-IV symptoms of PTSD. Respondents rate how much they were “bothered by that problem in the past month”. Items are rated on a 5-point scale ranging from 1 (“not at all”) to 5 (“extremely”). The PCL can be scored in several different ways. A total score (range 17-85) can be obtained by summing the scores from each of the 17 items. Although the CAPS was used initially for the study, it was decided by the research team with input from the funding agency that diagnosis of PTSD will be confirmed by referring clinician and eliminate stress of completing the interview for the veteran. For some of the veterans that are enrolled in the study, CAPS is available in their medical record. If it is available, we will abstract the information to further confirm the diagnosis.

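### The exploratory analysis of who benefits pairs chi-square with numeric outcome scores and then selects predictors at p<0.10 without allowing for the selection

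*Combined protocol and SAP*

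**What the plan says.** The analysis is in the combined protocol and SAP, under Data Management and Statistical Analysis, after the Hypothesis 1B text. Its purpose is stated as: "we will conduct an exploratory analysis to determine whether relationships exist between group status (SD vs. control), demographic variables" and the outcomes of interest, for which the text names the PCL-C and, as an example of psychosocial factors, community participation.

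The tests are assigned by type of demographic variable:
- Dichotomous: "Categorical demographic variables will be analyzed using a chi-square for variables that are dichotomous".
- Several categories: "one-way ANOVAs will be used for continuous variables that have multiple categories".
- Continuous: "Continuous demographic variables (e.g., age) will be compared to the outcomes using correlations", Pearson or Spearman according to distribution.

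The physical, psychosocial and economic variables are also correlated with the outcomes. Then: "Two separate multiple regression models will be developed using any variables significant" at p<0.10 in the univariate step. The regression outcomes come from 18 months and the predictors from baseline. The stated use is to describe the Veterans most likely to benefit compared with controls.

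On the outcome scales, the Measurements section says of the PCL: "A total score (range 17-85) can be obtained by summing the scores from each of the 17 items". The Hypothesis 1A text adds, of the PCL scores: "These scores are continuous". The Community Integration Questionnaire, which measures community participation, is described as ranging from 0 to 29.

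**The concern.** There are two separate weaknesses.

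First, a chi-square of gender against a PCL or CIQ score needs the score in categories, and no categories are given for this step. The analyst must either invent a cut or cross-tabulate gender against every observed score value. The ANOVA clause cannot be followed literally either, because a continuous variable does not have multiple categories. Real differences by a dichotomous characteristic may therefore be missed, and the result depends on an unstated choice.

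Second, a univariate p<0.10 decides what enters the regressions, and the regressions are then read as if their predictors had been chosen beforehand. No multiplicity control, shrinkage or validation is described. Selected predictors will look more reliable than they are.

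Determining who benefits most is part of Specific Aim 1, so the output will be read even though it is labelled exploratory.

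**Working it through.** The plan states no power or error rate for this analysis, so there is no figure to reproduce.

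**Inputs from the document.** Enrolment of up to 220 with 15% dropout leaves 220 × 0.85 = 187 (the text expects 200 completers). The screen is at p<0.10. Scales: PCL 17-85, CIQ 0-29.

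**Assumptions, not in the document.** PCL mean 55, SD 13; CIQ mean 15, SD 5; a true difference of 0 or 0.5 SD; a smaller category of 50%, 20% or 10% of Veterans; the number of candidate predictors.

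**1. Power of the test for a dichotomous demographic.** For a t-test at two-sided 0.10, power ≈ Φ(d/√(1/n1 + 1/n0) − 1.645). A median split of a normal score keeps 2/π = 0.64 of the information, so the first term is multiplied by √(2/π) = 0.798.
- 50% category: n1 = n0 = 93.5, and 0.5/0.1463 = 3.42. T-test: Φ(1.77) = 0.96. Median split: Φ(2.73 − 1.645) = 0.86.
- 20%: n1 = 37.4, n0 = 149.6, and 0.5/0.1828 = 2.74. T-test: 0.86. Median split: 0.70.
- 10%: n1 = 18.7, n0 = 168.3, and 0.5/0.2438 = 2.05. T-test: 0.66. Median split: 0.50.

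Simulation with rounded PCL scores (3000 runs per setting, n=187) agrees:

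| Smaller category | Chi-square, each score value | Chi-square, median split | t-test/ANOVA |
|---|---|---|---|
| 50% | 0.21 | 0.86 | 0.96 |
| 20% | 0.19 | 0.71 | 0.86 |
| 10% | 0.21 | 0.50 | 0.64 |

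At n=200 the median split gives 0.88, 0.73 and 0.51, against 0.97, 0.88 and 0.67.

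**2. Does the chi-square let in false predictors?** Same simulation with no true difference, PCL, n=187, in the order 50/20/10%. Share passing p<0.10:
- chi-square on each score value: 0.05/0.08/0.10
- median split: 0.11/0.10/0.09
- t-test/ANOVA: 0.10/0.10/0.10

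The largest rates in any setting were 0.13 for score values and 0.14 for the median split, both with a 10% category. The chi-square is mostly nominal or conservative, and changing the test leaves false entry near 0.10.

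**3. The p<0.10 screen.** With k null candidates, expected false entries per model are 0.1k, whether or not the candidates are independent. With independent candidates, the chance of at least one is 1 − 0.9^k.
- k = 4: 0.4 expected; 1 − 0.656 = 0.34
- k = 10: 1.0 expected; 1 − 0.349 = 0.65
- k = 20: 2.0 expected; 1 − 0.122 = 0.88

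The document does not count the candidates. Taking the items in Table 2 one by one and adding living arrangements gives about 19, so 20 is near the upper end.

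**4. What selection does to the final p-values.** A null variable that has passed p<0.10 has a chance of 0.05/0.10 = 0.5 of also having univariate p<0.05, against a nominal 0.05. Simulating the full procedure (3000 runs, 15 to 20 null candidates, n=65 and 187), 44-50% of the false entrants had p<0.05 in the final model when candidates were independent, and 19-24% when they were correlated at 0.3.

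**The case against.** The strongest defence is that the test sentence is only badly worded. It can be read as chi-square for dichotomous outcomes and ANOVA for continuous outcomes across categories. The same analysis also relates group status to demographics, where chi-square would be correct, and the Hypothesis 1B text does dichotomise 18-month function and participation. This does not rescue the sentence. No dichotomous outcome is named for this step, and the Hypothesis 1B model is a different analysis that goes on to say linear regression will be used. That model has its own screen at the same threshold ("Results from the previous hypotheses (1B) will be used to determine which predictor variables are entered into the regression model") and involves no chi-square.

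Other limits stand:
- Chi-square is assigned only to dichotomous variables. A reader might infer that all demographics are tested this way, but correlation covers age and, despite its wording, the ANOVA clause evidently covers variables with several categories.
- A reader might infer that the wrong test is what admits false predictors. The simulation does not support that; the 0.10 screen admits them.
- The remark that scores are continuous refers to the PCL alone. For participation the evidence is the 0-29 range.
- The 34-88% is a chance of entering a model, not of being reported as significant, and it depends on the assumed candidate count and on independence.
- A reader might infer that this regression feeds the Aim 3 recommendations. Aim 3 describes a consensus meeting on the study's findings and does not mention this analysis.

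**Conclusion.** The point holds as two separate, moderate defects in an analysis that the plan itself labels exploratory. The primary PCL mixed model is not affected.

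Chi-square does not fit numeric outcomes without a stated cut. Its cost is power: about 0.10 to 0.15 lost with a median split, and far more if every score value is its own category, under the assumed 0.5 SD difference and n=187. The p<0.10 screen admits 0.1 false predictors per null candidate per model, and the final p-values do not reflect the selection. The first result rests on assumed score distributions. The chance of at least one false entry rests on an assumed number of independent candidates, but the expected count per candidate does not need independence.

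One limit on interpretation belongs with this. The Design section eliminated the control group, so regressing 18-month scores on baseline variables among recipients shows who scores better or worse at 18 months. It cannot show who gains more from a dog than a control would.

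**What to change.** Replace the chi-square, ANOVA and correlation screen with one linear regression per outcome (PCL and CIQ). The 18-month score is regressed on the baseline score plus a short list of baseline predictors. The sponsor should choose that list, from variables already collected, and fix it before the 18-month outcomes are analysed. Dichotomous, multi-category and continuous predictors then all enter the same model, and no cut of the outcome is needed.

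Report every coefficient with its 95% interval, whatever its p-value, and label any predictor outside the list as post hoc. Describe the results as predictors of 18-month score among service dog recipients, and remove the comparison with control subjects from this paragraph.

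Replacing chi-square by a t-test alone would recover power but leave false entry near 0.10 per null variable. Tightening the screen to 0.05 would still leave a chance of at least one false entry of 1 − 0.95^k: 19%, 40% and 64% for 4, 10 and 20 independent null candidates.

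The cost is SAP wording, with no new data. The downside is that unexpected predictors can be reported only as post hoc.
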